1.2.7 Rationale for Time to Progression as a Primary Endpoint

Although vaccines have improved overall survival in mCRPC, they have not been shown to change short term TTP when used as monotherapy. Interestingly, similar findings were also seen with ipilimumab in melanoma [27]. Although this is not what is customarily seen with cancer treatments, it may be a characteristic of modern immune therapeutics [28]. An emerging mechanism to evaluate tumor growth rates using mathematical models may provide additional insight into this phenomenon [29, 30]. In a recent review of 5 NCI mCRPC trials including a vaccine trial, there appeared to be a sustained decrease in tumor growth rate in vaccine patients

Short Title: Enzalutamide Vaccine in mCRPC

Version Date: 03/29/2022

as compared to those treated with chemotherapy, who had transient reductions in tumor size, but then growth rate resumed at the same pre-treatment rate once cytotoxic therapy was discontinued. [31] This data suggests that a vaccine induced immune response may not decrease tumor size (or change TTP) but may lead to altered tumor growth rates which could have more substantial impact on overall survival [32]. (See **Figure 8**).

Furthermore, unpublished data from an ECOG PSA-TRICOM trial in non-metastatic prostate cancer demonstrated a reduced growth rate within 100 days of vaccine initiation [33]. Similarly, Sipuleucel-T has significantly prolonged PSA doubling time (another way to measure growth) after initial hormonal therapy in the same patient population [31]. Together, these data suggest that for patients getting combination therapy, disease can be controlled by standard therapies in the short term, while vaccines may impact tumor growth rates in the long term, ultimately resulting in prolonged TTP compared to standard therapy alone. (**Figure 8**)

If vaccines can alter growth rates and if cytoreductive therapies can reduce tumor burden, it would be reasonable to presume that vaccine combination therapies would potentially result in a TTP benefit.

[figure not shown]

Figure 8. Vaccine as part of combination therapy may improve TTP. Although vaccine as monotherapy may have no impact on short-term TTP, vaccine in combination regimens may improve TTP by altering the rate of regrowth as the effects of the companion therapy begin to diminish. If the companion therapy is cytoreductive, tumor volume will decrease, but as the therapeutic benefits wane, regrowth will occur. If sufficient time has passed to generate an immune response, the anti-tumor effects of the immune system may result in a delay in TTP (due to a slower re-growth rate) relative to cytoreductive treatment alone. [13]

1.3 SUMMARY OF RATIONALE

- 1) Enzalutamide is a well-tolerated, modern androgen receptor antagonist. Phase III trial have demonstrated a 4.8 month improvement in survival in mCRPC patients who were previously treated with docetaxel.
- 2) PROSTVACTTM is a novel candidate for prostate cancer immunotherapy. In a randomized controlled Phase 2 trial, PROSTVAC therapy was associated with a prolongation of survival by 8.5 months in men with metastatic castrate-resistant prostate cancer. The Phase 3 efficacy trial is on-going.
- 3) Preclinical data has demonstrated that hormonal therapies such as ARAs can enhance the immune response through multiple mechanisms. Specifically, the LTIB has shown that enzalutamide can increase thymic production of naïve T-cells, which could be activated by a cancer vaccine.
- 4) Data from the clinical trials with these therapies suggest that they are very well tolerated and without overlapping toxicity.

5) Data suggest that for patients getting combination therapy, TTP may be a reasonable clinical endpoint and such a finding could be important in determining the ultimate clinical role of therapeutic cancer vaccines.

Based on the above rationale, we will evaluate whether combining enzalutamide and PSA-TRICOM vaccine prolongs time to disease progression compared with enzalutamide alone in chemotherapy-naïve mCRPC.

2 ELIGIBILITY ASSESSMENT AND ENROLLMENT

2.1 ELIGIBILITY CRITERIA

2.1.1 Inclusion Criteria

2.1.1.1 Patients must have histologically or cytologically confirmed prostate cancer confirmed by either the Laboratory of Pathology at the NIH Clinical Center, Walter Reed National Military Medical Center at Bethesda prior to starting this study. If no pathologic specimen is available, patients may enroll with a pathologist's report showing a histological diagnosis of prostate cancer and a clinical course consistent with the disease.

2.1.1.2 Castrate testosterone level (<50ng/dl or 1.7nmol /L)

2.1.1.3 Metastatic disease documented by one of the following:

- Metastatic bone disease on an imaging study, or
- Soft tissue disease documented by CT/MRI, or

2.1.1.4 Progressive disease at study entry defined as one or more of the following criteria occurring in the setting of castrate levels of testosterone:

- i. Radiographic progression defined as **any new** or enlarging bone lesions or growing lymph node disease, consistent with prostate cancer
OR
- ii. PSA progression defined by sequence of rising values separated by >1 week (2 separate increasing values over a minimum of 2ng/ml (PCWG2 PSA eligibility criteria). If patients had been on flutamide, PSA progression is documented 4 weeks or more after withdrawal. For patients on bicalutamide or nilutamide disease progression is documented 6 or more weeks after withdrawal. The requirement for a 4-6 week withdrawal period following discontinuation of flutamide, nilutamide or bicalutamide only applies to patients who have been on these drugs for at least the prior 6 months. For all other patients they must stop bicalutamide, nilutamide or flutamide the day prior to enrollment.

2.1.1.5 Asymptomatic or mildly symptomatic from prostate cancer; no use of regularly scheduled opiate analgesics for prostate cancer-related pain

2.1.1.6 Patients must agree to continue to continuation of androgen deprivation therapy (ADT) with a gonadotropin-releasing hormone analogue/antagonist or bilateral orchiectomy

2.1.1.7 Age ≥ 18 years.

2.1.1.8 ECOG performance status ≤ 1 (Karnofsky $\geq 80\%$, see ([APPENDIX A](#))).

2.1.1.9 Patients must have normal organ and marrow function as defined below:

- absolute neutrophil count $\geq 1,500/\text{mcL}$
- platelets $\geq 100,000/\text{mcL}$
- total bilirubin within normal institutional limits; for patients with Gilbert's syndrome, total bilirubin $\leq 3.0\text{mg/dL}$
- AST(SGOT)/ALT(SGPT) $\leq 2.5 \times$ institutional upper limit of normal
- creatinine within 1.5 X normal institutional limits

OR

- creatinine clearance $\geq 60 \text{ mL/min}/1.73 \text{ m}^2$ for patients with creatinine levels above institutional normal by Cockcroft-Gault Equation

$$\text{creatinine clearance (mL/min)} = \frac{(140 - \text{age [y]}) \times \text{weight [kg]}}{(72 \times \text{serum creatinine [mg/dL]})} \times \text{Sex} \times \frac{\text{BSA [m}^2\text{]}}{1.73 \text{ m}^2}$$

In the equation above, the factor for "Sex" equals 0.85 for females and 1 for males

2.1.1.10 The effects of enzalutamide alone or in combination with PSA-TRICOM on the developing human fetus are unknown. For this reason, men must agree to use adequate contraception (hormonal or barrier method of birth control; abstinence) prior to study entry, for the duration of study participation and for three (3) months after the last dose of enzalutamide. Should a woman become pregnant or suspect she is pregnant while her partner is participating in this study, she should inform her treating physician immediately.

2.1.1.11 Ability of subject to understand and the willingness to sign a written informed consent document.

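### The renal eligibility limit is per 1.73 m2, but its formula is labelled mL/min and multiplies Cockcroft-Gault by BSA/1.73, so it overstates clearance for men with BSA above 1.73

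*Combined protocol and SAP*

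**What the plan says.** Protocol section 2.1.1.9 gives two renal routes into the trial, joined by OR. The first is "creatinine within 1.5 X normal institutional limits". The second is a creatinine clearance of at least 60 mL/min/1.73 m2 "for patients with creatinine levels above institutional normal by Cockcroft-Gault Equation".

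The formula printed beneath has a left-hand side that begins "creatinine clearance (mL/min", with no per-1.73 m2 in the unit. Its right-hand side is (140 − age) × weight / (72 × serum creatinine), times a sex factor, times BSA/1.73. The only explanation that follows is that "the factor for 'Sex' equals 0.85 for females and 1 for males". Nothing else in the document explains the BSA term or reverses it.

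**The concern.** The limit carries one unit, the formula carries another, and the size factor converts to neither. The weight-based term is an absolute clearance in mL/min. A value per 1.73 m2 requires multiplication by 1.73/BSA. A value in mL/min requires no size factor. The printed BSA/1.73 raises the result for any man with BSA above 1.73, whose weight is already in the numerator.

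The second route decides eligibility only when creatinine exceeds 1.5 times normal, which is where renal function is in doubt. Followed as written, the rule can admit a man whose clearance is below 60 in either unit. Section 5.1 requires records confirming that each patient met each criterion. For a man admitted this way, that confirmation rests on a figure that is in neither unit.

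**Working it through.** **Inputs from section 2.1.1.9.** Limit 60 mL/min/1.73 m2; base term CG = (140 − age) × weight / (72 × creatinine), in mL/min; sex factor 1 (all participants are men); printed size factor BSA/1.73; alternative route, creatinine within 1.5 times normal. The plan gives no worked value to reproduce.

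**Assumptions.** The document gives neither an upper limit of normal (ULN) for creatinine nor a BSA formula. I take ULN 1.2 to 1.35 mg/dL, so 1.5 × ULN is 1.8 to 2.025, and BSA = √(height in cm × weight in kg / 3600). Ages, heights and weights are illustrative.

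**Step 1: what a printed 60 means.** Printed value P = CG × BSA/1.73. Therefore
- in mL/min: CG = P × 1.73/BSA;
- per 1.73 m2: CG × 1.73/BSA = P × (1.73/BSA)².

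| BSA (m2) | Printed factor | P = 60 in mL/min | P = 60 in mL/min/1.73 m2 |
|---|---|---|---|
| 1.73 | 1.000 | 60.0 | 60.0 |
| 1.9 | 1.098 | 54.6 | 49.7 |
| 2.0 | 1.156 | 51.9 | 44.9 |
| 2.1 | 1.214 | 49.4 | 40.7 |
| 2.2 | 1.272 | 47.2 | 37.1 |
| 2.4 | 1.387 | 43.2 | 31.2 |

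The overstatement is BSA/1.73 if the limit was meant in mL/min (16% at BSA 2.0, 27% at 2.2). It is (BSA/1.73)² if the limit was meant per 1.73 m2 (34% and 62%).

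**Step 2: one man.** Assume age 65, 100 kg, 178 cm, creatinine 2.0 mg/dL, so BSA = √(178 × 100/3600) = 2.22.
- CG = 75 × 100 / (72 × 2.0) = 52.1 mL/min.
- Printed: 52.1 × 2.22/1.73 = 66.9, so he passes.
- Per 1.73 m2: 52.1 × 1.73/2.22 = 40.5.

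He is below 60 in both units and passes only on the printed formula. The creatinine route does not admit him if ULN is below 2.0/1.5 = 1.33 mg/dL.

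**Step 3: who is exposed once the OR is applied.** Take height 178 cm and age 70.
- Creatinine 1.8: P = 70w/(72 × 1.8) × √(178w/3600)/1.73, which is 0.0694 × w^1.5. This reaches 60 at about 91 kg.
- Creatinine 2.04 (just above 1.5 × 1.35): P = 0.0613 × w^1.5, which reaches 60 at about 99 kg.

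At these thresholds the clearance is about 47 to 49 mL/min, or 37 to 40 mL/min/1.73 m2. At age 80 the passing weight is about 101 to 110 kg.

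**Step 4: small men.** Below BSA 1.73 the printed value is too low. To be wrongly excluded, a man needs creatinine above 1.5 × ULN and a true clearance of at least 60.
- BSA 1.6, 160 cm (57.6 kg), creatinine 1.8, per 1.73 m2: CG must be 60 × 1.6/1.73 = 55.5, so 140 − age = 55.5 × 72 × 1.8/57.6 = 125, or age 15.
- The most lenient edge, BSA 1.73, 160 cm (67.3 kg): 140 − age = 60 × 129.6/67.3 = 115.5, or age 24.

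This does not arise in a prostate cancer population.

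**The case against.** The inconsistency itself is hard to defend. BSA/1.73 would be the right factor for turning a clearance already expressed per 1.73 m2 into mL/min, which matches the label. But the Cockcroft-Gault term is not so expressed, and the result would still not be in the unit of the limit.

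The stronger objections concern reach, and most of them stand.

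- **Which part is the slip.** A reader might infer that the formula must become 1.73/BSA and that the error is therefore the squared factor. The documents do not settle this. The mL/min label and the reference to Cockcroft-Gault equally support an mL/min limit with no BSA term, in which case the error is BSA/1.73.
- **Small men.** A reader might infer that they are wrongly kept out. Step 4 shows that the creatinine route makes this practically impossible.
- **The BSA 2.0 row.** At 178 cm (80.9 kg) and creatinine 1.8, a printed 60 needs 140 − age = 51.9 × 129.6/80.9 = 83, or age 57 or under. For older men the exposed group is heavier.
- **Enrolment and results.** A reader might infer that correcting the formula would change who enters, or that ineligible men were enrolled. Section 6.5.2 records closure to accrual on 12/20/2016, and nothing shows that any man used this route. Nor does anything link the formula to randomisation, the log-rank comparison or power.
- **Transcription.** The equation was read from a PDF by a program. If the source page shows 1.73/BSA, only the disagreement between label and limit remains.

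None of this removes the wrongful-admission case: the man in Step 2 fails in both units and passes as printed.

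**Conclusion.** The point holds in limited form. Section 2.1.1.9 combines a per-1.73 m2 limit, an mL/min label and a BSA/1.73 factor that cannot all be right. Subject to confirming the fraction on the source page, the printed formula overstates clearance for every man with BSA above 1.73, by 16% or 34% at BSA 2.0 and by 27% or 62% at BSA 2.2, depending on the unit intended.

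The practical consequence is confined to heavier men with creatinine above 1.5 times normal. The weight thresholds rest on the assumed height, upper limit of normal and BSA formula. The number affected cannot be known from the documents and is probably small among the 72 planned evaluable men. It is an error in an eligibility rule worth correcting and rechecking; it does not by itself call the trial's comparison into question.

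**What to change.** 1. Check the orientation of the BSA fraction against the source page.
2. Reconcile the unit of the limit, the label of the formula and the BSA factor. If the per-1.73 m2 unit is kept, the factor must be 1.73/BSA and the label mL/min/1.73 m2. If the limit is meant in mL/min, the BSA factor must be dropped and the limit restated in that unit. Which applies is the sponsor's decision.
3. Identify any man whose creatinine exceeded 1.5 times normal at entry, recompute his clearance with the reconciled formula, and list those below the reconciled limit as eligibility deviations (section 7.8).

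The cost is a one-line text correction and a short record check. Height and weight are baseline items (section 2.4.1), and age and creatinine were already needed to apply the criterion. No new data and no change to the analysis are required.

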3.3.3 Criteria for individual patient re-treatment

3.3.3.1 Patients with grade 3 non-autoimmune toxicity due to the treatment regimen, may resume treatment provided that the toxicity has decreased to baseline or grade 2 toxicity within 60 days from the last day of treatment. See section **3.6.1** Criteria for removal from protocol therapy.

3.3.3.2 Patients receiving vaccine with \geq grade 3 autoimmune toxicity will not be treated and will be removed from study.

3.3.3.3 Patients who develop any grade 4 toxicity attributable to protocol treatment will be removed from the protocol treatment and followed for resolution of toxicity

3.3.3.4 Patients who develop grade 3 injection site reactions will have their vaccine held until injection site reaction resolves to grade 2 or less.

3.3.3.5 If a scheduled vaccine dose is missed due to scheduling or logistical issues, the vaccine may be given within 14 days of the appointed time.

Short Title: Enzalutamide Vaccine in mCRPC

Version Date: 03/29/2022

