3.6 CRITERIA FOR REMOVAL FROM PROTOCOL THERAPY AND OFF STUDY CRITERIA

3.6.1 Criteria for removal from protocol therapy

- Disease progression as evidenced by radiographic or clinical progression (defined in section [5.3.5](#)).
- Intercurrent illness or medical circumstances: if at any time the constraints of this protocol are detrimental to the patient's health, the patient may be removed from protocol therapy. In this event, the reasons for withdrawal will be documented.
- Patient's request to be taken off study. In this event, the reasons for withdrawal will be documented.
- If patients are non-compliant with the protocol guidelines, they may be removed from the study at the discretion of the principal investigator.
- Any Grade 4 toxicity that is possibly, probably or definitely related to the protocol treatment will require a patient to be off-treatment.
- Grade ≥ 3 autoimmune toxicity while on vaccine, will require a patient to be off-treatment.
- Any Grade 3 non-autoimmune toxicity that does not resolve to Grade 1 or baseline within 60 days and is possibly, probably or definitely related to the protocol treatment will require a patient to be off-treatment.
- Any grade of seizure will require discontinuation of enzalutamide but patients may continue vaccine at the discretion of the investigator.

Prior to documenting removal from protocol therapy, effort must be made to have all subjects complete a safety visit approximately 30 days following the last dose of study therapy.

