6.5.2 Safety Monitoring Committee (SMC)

This protocol will be periodically reviewed by an intramural Safety Monitoring Committee (SMC). Initial review will occur as soon as possible after the annual NIH Intramural IRB continuing review date. Subsequently, each protocol will be reviewed as close to annually as the quarterly meeting schedule permits or more frequently as may be required by the SMC based on the risks presented in the study. For initial and subsequent reviews, protocols will not be reviewed if there is no accrual within the review period.

The SMC review will focus on unexpected protocol-specific safety issues that are identified during the conduct of the clinical trial.

Written outcome letters will be generated in response to the monitoring activities and submitted to the Principal investigator and Clinical Director or Deputy Clinical Director, CCR, NCI.

SMC concluded their oversight of the study on 12/20/2016 when the study closed to accrual.

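### In 2.1.1.9 the clearance formula, if the page reads as extracted, has its body-surface factor inverted for a limit per 1.73 m2; 3.3.3.1/3.6.1 and the contraception periods also need small alignments

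*Combined protocol and SAP*

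**What the plan says.** **Renal eligibility (2.1.1.9).** There are two routes, joined by OR. The first is "creatinine within 1.5 X normal institutional limits". The second is a clearance of at least 60 mL/min/1.73 m2 "for patients with creatinine levels above institutional normal by Cockcroft-Gault Equation". The equation that follows is labelled "creatinine clearance (mL/min" and, as extracted, is the usual Cockcroft-Gault expression times a sex factor (1 for men) times BSA/1.73.

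**Accrual (6.5.2).** "SMC concluded their oversight of the study on 12/20/2016 when the study closed to accrual".

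**Restart and removal after grade 3 non-autoimmune toxicity.** Under 3.3.3.1 such patients "may resume treatment provided that the toxicity has decreased to baseline or grade 2 toxicity within 60 days from the last day of treatment", and the text adds "See section 3.6.1 Criteria for removal from protocol therapy". Section 3.6.1 lists "Any Grade 3 non-autoimmune toxicity that does not resolve to Grade 1 or baseline within 60 days" as a reason for removal where the toxicity is at least possibly treatment-related, and it is mandatory: it "baseline within 60 days and is possibly, probably or definitely related to the protocol treatment will require a patient to be off-treatment" (the quotation starts mid-sentence). Section 3.6.1 gives no day from which its 60 days are counted.

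**Contraception.** Sections 2.1.1.10 and 7.6.1 set the end at 3 months after the last enzalutamide dose. Sections 13.1.2 and 13.2.10.1 tell vaccinated men not to father a child for at least 4 months after vaccine therapy.

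**The concern.** Cockcroft-Gault gives an absolute clearance in mL/min. To compare it with a limit per 1.73 m2, it must be multiplied by 1.73/BSA. Multiplying by BSA/1.73 would be right only to turn an already indexed value back into mL/min, and this value is not indexed. The extracted result is therefore neither mL/min nor mL/min/1.73 m2. It loosens the limit for men larger than 1.73 m2 and tightens it for smaller men. What is at stake is whether any large man with raised creatinine was enrolled below the stated limit.

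The toxicity sections use different grades for the same 60-day window: grade 2 is enough to restart, but grade 1 or baseline is needed to avoid removal. The contraception sections give different end dates to an Arm B man. Unlike the formula, these two points can still bear on men on or recently off treatment.

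**Working it through.** **Inputs from the documents:** the limit of 60 mL/min/1.73 m2, the factor BSA/1.73, the label mL/min, sex factor 1, and the alternative route at 1.5 x normal, all from 2.1.1.9. **Assumed, because the documents give none:** BSA = sqrt(cm x kg/3600) in the weight search, a height of 180 cm, ages 60 to 80, and upper normal creatinine limits of 1.1 to 1.4 mg/dL.

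**Size of the error.** With C = (140 - age) x kg/(72 x creatinine):
- as extracted: C x BSA/1.73
- indexed: C x 1.73/BSA
- ratio: (BSA/1.73)^2

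| BSA (m2) | Extracted/indexed | Indexed limit really applied, 60 x (1.73/BSA)^2 |
|---|---|---|
| 1.6 | 0.86 | 70.1 |
| 2.0 | 1.34 | 44.9 |
| 2.2 | 1.62 | 37.1 |

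**Example (assumed values):** age 70, 100 kg, BSA 2.2 m2, creatinine 2.0 mg/dL. He needs the formula if the upper normal limit is below 2.0/1.5 = 1.33 mg/dL.
- C = 70 x 100/(72 x 2.0) = 48.6 mL/min: fails 60.
- As extracted: 48.6 x 2.2/1.73 = 61.8: passes.
- Indexed: 48.6 x 1.73/2.2 = 38.2: fails.

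He passes on the extracted formula and fails on either coherent reading.

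**Who could be affected.** Creatinine is set 0.01 mg/dL above 1.5 x the upper limit, at 180 cm and age 70. Lowest passing weight in a search from 50 to 180 kg:

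| Upper limit (mg/dL) | As extracted | Unindexed | Indexed |
|---|---|---|---|
| 1.1 | 86 kg | 103 kg | 176 kg |
| 1.2 | 91 kg | 112 kg | none |
| 1.3 | 96 kg | 121 kg | none |
| 1.4 | 101 kg | 131 kg | none |

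At age 60 the extracted cut-offs are 79 to 92 kg (90 to 114 unindexed). At age 80 they are 95 to 112 kg (120 to 152 unindexed). Indexed clearance at the extracted cut-offs runs from 46 (age 60, limit 1.1) down to 32 (age 80, limit 1.4).

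**Comparison with the other route.** Take a 70 kg, 180 cm man with creatinine exactly at 1.5 x the limit, who is eligible without the formula; his BSA is sqrt(180 x 70/3600) = 1.87 m2.
- Age 60, limit 1.1: C = 80 x 70/(72 x 1.65) = 47.1; indexed 47.1 x 1.73/1.87 = 44.
- Age 80, limit 1.4: C = 60 x 70/(72 x 2.10) = 27.8; indexed 27.8 x 1.73/1.87 = 26.

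In all 12 age-by-limit cells this man's indexed clearance is below that of the man who just passes the formula.

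**Day-60 rules side by side.** Day 60 is counted in both sections from the last treatment day, and the toxicity was a related grade 3:

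| State at day 60 | 3.3.3.1 | 3.6.1 |
|---|---|---|
| Grade 1 or baseline | within the permission on any sensible reading | stays on |
| Grade 2, baseline grade 2 | may resume | stays on (back to baseline) |
| Grade 2, baseline below grade 2 | may resume | must come off |
| Grade 3 | may not resume | must come off (unless baseline) |

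Only the third row differs.

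**Contraception.** If both agents stop on the same day, the enzalutamide period ends 4 - 3 = 1 month before the vaccine period. The gap closes if the last vaccine dose came at least 1 month before the last enzalutamide dose.

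**The case against.** **The equation is machine-read.** This stands as a condition. The extraction is complete, with units and an explicit fraction, but the page must be checked before anything is amended.

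**The formula hardly matters.** Most of this stands. Men with creatinine within 1.5 x normal never reach it, and that route accepts indexed clearances of 26 to 44 in the example above. The enzalutamide and vaccine information in section 13 as supplied gives no renal dose rule or renal contraindication. Accrual is closed, so a corrected formula admits or refuses nobody. A reader might infer that unsafe or ineligible men were enrolled. The documents do not support that: they report no patient's creatinine, and the low clearances the formula lets through are ones the other route accepts openly. What remains is that the stated rule does not compute the quantity its own limit refers to.

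**The toxicity rules already work together.** This largely stands. A reader might infer that 3.3.3.1 and 3.6.1 contradict each other. But 3.3.3.1 is a permission that points to 3.6.1, and 3.6.1 is mandatory, so the natural reading is that removal prevails. A man can restart at grade 2 and then be held to grade 1 or baseline by day 60. The unexplained grade difference and the undefined start in 3.6.1 remain.

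**Other eligibility gaps.** A reader might add that list 2.1.2 names no hepatitis B/C exclusion and covers only symptomatic heart failure. Section 11.1.2 states the hepatitis exclusion and 2.2 tests for both viruses; 13.2.11 states the wider cardiac exclusion. These are questions of placement, with no effect now that accrual is closed.

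**Contraception.** Arm B men are given the longer period in section 13, and the vaccinia patient instruction sheet (Appendix B) was not available to check. What patients are actually told therefore cannot be judged, but the protocol sections still disagree.

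**Conclusion.** Subject to the page check, the formula in 2.1.1.9 is wrong as written, and the error is minor. It misstates indexed clearance by (BSA/1.73)^2, which moves a nominal limit of 60 to about 45 at 2.0 m2 and 37 at 2.2 m2. Those figures need no patient assumptions; the weight cut-offs depend on the assumed height, BSA formula and upper normal limits. The reach is confined to men with entry creatinine above 1.5 x normal, and the remaining question is only whether any enrolled man fell below the stated limit.

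The day-60 point is a clarification. It concerns only a man at grade 2 on day 60, after a related grade 3 non-autoimmune toxicity, whose baseline was below grade 2. The documents give no count of such men. The contraception difference is a real mismatch of up to 1 month when both agents stop together, and it can still affect Arm B men.

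None of this touches power, alpha or sample size, and no effect on censoring or arm balance is claimed.

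**What to change.** 1. Check the equation in 2.1.1.9 against the original page. If it reads as extracted, change the factor to 1.73/BSA and the label to mL/min/1.73 m2. The limit of 60 stays.
2. Recompute clearance only for enrolled men whose entry creatinine exceeded 1.5 x normal, and report any below 60.
3. In 3.3.3.1, keep restart at grade 2 and add that it is subject to removal under 3.6.1 if the toxicity is not at grade 1 or baseline within 60 days. In both sections, start the 60 days at the last day of treatment before the hold.
4. In 2.1.1.10 and 7.6.1, set the end of contraception at the later of 3 months after the last enzalutamide dose and 4 months after the last vaccine dose, to match 13.1.2 and 13.2.10.1.

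The cost is one wording amendment and a record check limited to one small, identifiable group. No assessment is added. Item 3 changes the outcome for nobody if 3.6.1 is already read as governing. Item 4 lengthens contraception by at most 1 month for an Arm B man who stops both agents together. Adding hepatitis B/C and the wider cardiac exclusion to list 2.1.2 is optional tidying.
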